6.1.5.4 Follow-up Visits

Subjects who discontinue trial treatment for a reason other than disease progression will move into the Follow-Up Phase and should be assessed every 12 weeks (84 ± 7 days) by complete blood count to monitor disease status. Every effort should be made to collect information regarding disease status until the start of new anti-neoplastic therapy, disease progression, death, or end of the study or up to 5 years from enrollment. Information regarding post-study anti-neoplastic treatment will be collected if new treatment is initiated.

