3.2 Rationale

3.2.1 Rationale for the Trial and Selected Subject Population

Acute myeloid leukemia (AML) is a malignant hematopoietic disorder characterized by the unregulated growth of myeloid precursors (blasts) and associated marked reduction in normal hematopoiesis. It is the most common acute leukemia in adults, with an estimated 18,860 new cases of AML diagnosed per year in the United State and 10,460 deaths. [23] Disease related morbidity and mortality arise from cytopenias, leading to complications such as bleeding and/or infection, as well as end organ damage from the circulating blasts. If left untreated, AML can lead to death within weeks. [24]

The standard treatment for newly diagnosed AML consists primarily of an anthracycline combined with a nucleoside analogue, cytarabine. The goal of remission induction chemotherapy is the rapid restoration of normal bone marrow function. [25] Once a complete remission is attained, relapse invariably occurs without additional consolidation therapy. Consolidation approaches are based on prognosis and age, but may include 1-4 cycles of high dose cytarabine chemotherapy or allogeneic stem cell transplant. While consolidation therapy reduces relapse, up to 50% of younger patients still relapse. [26]

Although standard therapeutic approaches are tailored to younger patients, the median age of diagnosis of acute myelogenous leukemia (AML) is 67 years. [27] Unfortunately, the outcomes for patients older than 60 years are quite poor. Population studies in AML report 5-year survival rates of 3% to 8% compared to up to 50% for younger patients. [28] Intensive induction therapy, as described above, remains the standard of care for those elderly patients who are able to tolerate it, but rates of complete remission (CR) range from 20% to 60% dependent on the number of adverse prognostic conditions present. [29] The 2-year DFS of patients ≥ 60 yrs of age with AML who undergo induction therapy has been consistently at 24-26% in two large studies conducted in 2001 and 2010. [30; 31] Unfortunately, there have been no important advances in induction therapy since then.

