| Treatment Cycle/Title: | Main Study Screening | 1 | 2 | 3 | 4 | To be repeated beyond 8 cycles | | | | Discon | Safety Follow-up | Follow Up Visits ^b | Survival Follow-Up |
| | | | | | | 5 | 6 | 7 | 8 | | | | |
| Scheduling Window (Days): | -28 to -1 | | ± 3 | ± 3 | ± 3 | ± 3 | ± 3 | ± 3 | ± 3 | At time of Discon | 30 days post discon | Every 12 weeks post discon | Every 12 weeks |
| T3, FT4 and TSH | X ^d | | X | | X | | X | | X | X | X | | |
| Chest radiograph | X | | | | | | | | | | | | |
| Bone marrow biopsy | X ^e | | | | | | | | X ^f | X ^f | | | |
| Archival or Newly Obtained Tissue Collection | X ^g | | | | | | | | | | | | |
| Correlative Studies Blood Collection ^h | | X | X | | X | | | | X ^h | X | | | |

a: Treatment cycles occur every 3 weeks, but may be given +/- 3 days of the scheduled dose. See Section 6.1.5.2

b: Follow-up CBC with differential should occur every 12 weeks +/- 7 days after discontinuation of therapy until disease progression, initiation of new anti-neoplastic therapy, death, end of study, re-treatment with pembrolizumab., or a total of 5 years from the subject's enrollment.

c: Pregnancy tests must occur within 72 hours of the first dose of pembrolizumab

d: All screening laboratory assessment must occur within 10 days prior to the first treatment

e: The screening bone marrow biopsy must be performed and read by a UPMC hematopathologist within 4 weeks prior to the 1st treatment cycle, and include flow cytometry and cytogenetic assessment. If possible, the screening bone marrow biopsy should be sent to the Fred Hutchinson Cancer Center for multiparameter flow cytometric minimal residual disease testing.

f: Bone marrow biopsy for efficacy assessment should occur at one year (between treatment cycle 16-18), and at treatment discontinuation (due to completion of 2 years, toxicity, or relapse) and include flow cytometry and cytogenetic assessment.

g: Subject should be assessed for achieved marrow or peripheral leukemic blasts from diagnosis of AML at screening visit

h: Correlative blood draws may be collected up to two (2) days prior to dosing. Blood collection for correlative studies should occur prior to cycle 1, 2, 4, 8, 17 (+/-1 treatment cycle), and at disease progression or the end of 2 years of treatment, whichever comes first.

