6.1.5.3 Post-Treatment Visits

6.1.5.3.1 Safety Follow-Up Visit

The mandatory Safety Follow-Up Visit should be conducted approximately 30 days after the last dose of trial treatment or before the initiation of a new anti-cancer treatment, whichever comes first, as described in Section 6.0. All AEs that occur prior to the Safety Follow-Up Visit should be recorded. Subjects with an AE of Grade > 1 will be followed until the resolution of the AE to Grade 0-1 or until the beginning of a new anti-neoplastic therapy, whichever occurs first. SAEs that occur within 90 days of the end of treatment or before initiation of a new anti-cancer treatment should also be followed and recorded.

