7.2 Statistical Analysis Plan Summary

7.2.1 Primary Efficacy Objective: *To evaluate the time to relapse (TTR) in patients > 60 years with AML in complete remission undergoing post-remission therapy with pembrolizumab.* The time to relapse function will be estimated by the product-limit (Kaplan-Meier) method, with an appropriate 80% confidence interval. Death is considered a censoring event in determining TTR.

The median TTR will also be estimated, along with an appropriate confidence interval. Assuming an exponential time to failure distribution, 26% two-year TTR under the standard induction therapy is associated with a median of 12.3 months. The null hypothesis that the treatment with pembrolizumab offers no increase in TTR will be tested by determining if 12.3 months is within an 80% confidence interval around the median, a one-sided $\alpha=0.10$ test. The sensitivity of the treatment of death as a censoring event will be assessed by repeating the above analysis on relapse-free survival, where death and relapse are both considered events. Patients who drop out of the study will be treated as censored at the last observation time.

Potential prognostic factors for TTR in this population will also be explored. These include the use of consolidation therapy (0 vs 1-4), cytogenetic risk category (high-risk, intermediate risk, or low risk), FLT3 status (FLT3-ITD mutation present or absent), NPM1 status (NPM1 mutation present or absent), age >70 years, minimal residual disease, and ECOG performance status. The survival distributions for TTR will be computed using the Kaplan-Meier method and the log-rank test used to test for statistical differences in the distributions for the aforementioned exposure groups. Multivariate analysis using Cox regression will then be used to adjust for all significant covariates. Patients who drop out of the study will be treated as censored at the last observation time. Patients with missing covariate data will be excluded from this exploratory analysis.

7.2.2 Primary Safety Objective: *To evaluate the safety and tolerability of pembrolizumab in patients > 60 years with AML.* The NCI CTCAE type and grade of adverse events and their association with treatment will be tabulated. Section 8.3 contains a stopping rule for excess toxicity.

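### Section 7.2.1 censors every death in the primary TTR analysis, so an AML death before relapse is documented counts as relapse-free; 12-weekly counts after drug is stopped make this more likely

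*Combined protocol and SAP*

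**What the plan says.** **Monitoring on drug.** The flow chart (5.1) marks a blood count at every cycle, and footnote a states: "Treatment cycles occur every 3 weeks, but may be given +/- 3 days of the scheduled dose".

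**Monitoring after a non-relapse stop.** A marrow is done "at treatment discontinuation (due to completion of 2 years, toxicity, or relapse) and include flow cytometry and cytogenetic assessment" (5.1, footnote f). "The mandatory Safety Follow-Up Visit should be conducted approximately 30 days after the last dose of trial treatment" (6.1.5.3.1), and the flow chart marks a blood count there. After that, patients "should be assessed every 12 weeks (84 ± 7 days) by complete blood count to monitor disease status" (6.1.5.4; footnote b of 5.1 agrees). No marrow is marked in the follow-up columns. Footnote f ties the one-year marrow to cycles 16-18. Section 6.1.2.6 asks for one after a year without mentioning dosing, so whether it applies off drug is unclear.

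**Analysis.** Section 7.2.1 says: "Death is considered a censoring event in determining TTR". It adds RFS, with death and relapse both as events, as the check on that choice. Section 12.3 defines relapse by blasts in blood or marrow. No section says how to treat an AML death without a documented relapse. Section 3.2.3.1.1 defines TTR as survival without relapse, under which a death would not be censored.

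**The concern.** Censoring at death treats the patient as having been at the same risk of later relapse as those still followed. For a patient who died of unrecorded relapse that is wrong, because the event has already happened. The protocol itself says of the disease: "If left untreated, AML can lead to death within weeks". A 12-week gap between counts could therefore contain both relapse and death.

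The trial has one arm and a fixed null median, so no concurrent arm shares the error. Each relapse lost in this way lengthens the estimated TTR and makes it easier for the confidence interval to clear 12.3 months. The losses fall mainly on patients who stopped drug without relapse, including those who stopped for toxicity.

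**Working it through.** **1. The plan's own figures.** Null median: 24 × ln 2 / (−ln 0.26) = 12.35 months, against 12.3 stated. Power at a true median of 19.5 months, with 24 months' follow-up per patient: expected relapses 40 × (1 − exp(−24 ln 2 / 19.5)) = 23.0; Φ(√23.0 × ln(19.5/12.35) − 1.28) = 81.8%, against 80% stated. Other follow-up assumptions give 76-86%.

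**2. Detection delay.** If relapse falls evenly within a gap, the mean delay is half the gap: 6 weeks for 12-weekly counts and 1.5 weeks for 3-weekly. The excess is 4.5 weeks, or about 1.03 months per off-drug relapse (maximum 12 − 3 = 9 weeks). Including the 30-day count lowers the off-drug mean to about 5.7 weeks.

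**3. Chance that death precedes the next count.** With exponential survival after relapse (median m) and gap g, let λ = ln 2 / m. The probability is 1 − (1 − e^(−λg)) / (λg). Assume m = 8 weeks and no unscheduled detection:
- g = 12 weeks: λg = 1.040, probability 0.38.
- g = 3 weeks: λg = 0.260, probability 0.12.

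For medians of 4, 2 and 1 months, a simulation that includes the 30-day count loses 19%, 33% and 52% of off-drug relapses.

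**4. Inputs missing from the documents.** Neither the rate of stopping without relapse nor the time from relapse to death is given. The nearest figure in 3.1.2 is 9.4% stopping for an adverse event in a solid-tumor trial. The ranges below are assumptions.

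**5. False-positive rate.** Simulated trials of 40 with exponential relapse at the null median, rejecting when the lower 80% log-log limit for the median exceeds 12.3 months. The 30-day count is included, and only off-drug relapses can be lost:

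| Off drug by month 12 | 10% | 20% | 30% |
|---|---|---|---|
| 3-weekly counts throughout, no relapse lost | 0.11 | 0.11 | 0.11 |
| Plan, 8-week survival, no unscheduled detection | 0.13 | 0.16 | 0.18 |
| Same, 80% of fatal relapses recognised | 0.12 | 0.13 | 0.13-0.14 |

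Counting the lost deaths as events returns the rate to about 0.11-0.12 across these scenarios. Section 7.2.1 does not name the type of confidence limit. In a parallel run at 20% stopping, moving from no lost deaths to a 2-month median survival raised the rate from 0.107 to 0.141 with log-log limits, and from 0.179 to 0.193 with plain limits. The direction is the same and the step is smaller.

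**6. Apparent median, true value 12.3 months.** With 3-weekly counts throughout and no lost deaths it is 12.64. Under the plan, late dating alone gives 12.73, 12.83 and 13.02 at 10%, 20% and 40% stopping, an excess of 0.1 to 0.4 months. At 20% stopping, with deaths censored and median survival of 4, 2 or 1 months:
- Plan: 13.04, 13.21, 13.45.
- 3-weekly counts off drug, deaths still censored: 12.72, 12.79, 12.92.
- Plan's schedule, analysed as RFS: 12.79, 12.76, 12.72.

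**The case against.** A reader might infer that relapse off drug is sought by nothing except a 12-weekly count. The documents do not support that. There are a marrow at discontinuation and a count at 30 days, Section 6.1 allows unscheduled procedures, and 6.1.5.4 asks for every effort to collect disease status. For 90 days after treatment, serious adverse events are reported (6.2.3.1), and progression leading to hospitalization or death is an adverse event.

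A reader might also infer that relapses will be lost in numbers. That is assumed. Section 12.3 does not require a scheduled visit to find the blasts, and the remark about death within weeks describes untreated AML in general, not relapse in monitored patients. If most fatal relapses are recognised, little remains beyond the late-dating effect.

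A third tempting inference is that late dating favours the drug. The comparison is with a historical value whose assessment schedule the documents do not give, so the net direction cannot be stated.

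Finally, RFS is already planned and removes the lost-death effect almost entirely. That is true, but the null hypothesis is tested on TTR. RFS also counts every death, so a difference between the two results would not show whether missed relapse or unrelated death caused it.

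What stands is the rule itself: an AML death without a documented relapse is censored, and no passage provides otherwise.

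**Conclusion.** The point holds in a limited form. Censoring all deaths biases primary TTR upward whenever an AML death precedes documentation of relapse, and the longer interval between counts off drug makes this more likely. Under assumed stopping of 10-30% by month 12, 8-week median survival and no unscheduled detection, the false-positive rate is about 0.13-0.18, against about 0.11 with 3-weekly counts and no losses and a nominal 0.10. With 80% recognition it is about 0.12-0.14. The upper figures are therefore a bad case, not a forecast. Late dating alone is minor beside the target difference of 19.5 − 12.3 = 7.2 months. The change is worth making because it is cheap and because Sections 3.2.3.1.1 and 7.2.1 disagree about what a death means for the primary endpoint.

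**What to change.** **In 7.2.1,** replace the blanket rule. A death attributed to AML, or a death of undetermined cause in a patient still in disease follow-up, is a relapse event on the date of death. Only a death attributed to another cause is censored. Write the attribution criteria before analysis, since the trial is open-label.

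**Dating.** Date relapse at the earliest documented evidence, including counts from usual care between visits, and record these on the case report form.

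**Definition.** Reconcile the TTR definition in 3.2.3.1.1 with 7.2.1. Keep RFS as the sensitivity analysis.

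A rule requiring a clean count within 12 weeks of death would be a poor substitute. With visits at 84 ± 7 days, two on-schedule counts can be 84 + 14 = 98 days apart, so non-leukemic deaths in compliant patients would become relapses.

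**Cost.** A few sentences, a cause-of-death field and a field for outside counts, with no new visit or procedure. A few deaths of unknown cause will count as relapses, making TTR slightly less favourable.

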6.1.5.4.1 Survival Follow-up

Once a subject experiences confirmed disease progression or starts a new anti-cancer therapy, the subject moves into the survival follow-up phase and should be contacted by telephone every 12 weeks to assess for survival status until death, withdrawal of consent, or the end of the study, whichever occurs first.

6.2 Assessing and Recording Adverse Events

An adverse event is defined as any untoward medical occurrence in a patient or clinical investigation subject administered a pharmaceutical product and which does not necessarily have to have a causal relationship with this treatment. An adverse event can therefore be any unfavorable and unintended sign (including an abnormal laboratory finding, for example), symptom, or disease temporally associated with the use of a medicinal product or protocol-specified procedure, whether or not considered related to the medicinal product or protocol-specified procedure. Any worsening (i.e., any clinically significant adverse change in frequency and/or intensity) of a preexisting condition that is temporally associated with the use of the investigational product, is also an adverse event.

Changes resulting from normal growth and development that do not vary significantly in frequency or severity from expected levels are not to be considered adverse events. Examples of this may include, but are not limited to, teething, typical crying in infants and children and onset of menses or menopause occurring at a physiologically appropriate time.

Adverse events may occur during the course of the use of the investigational product in clinical trials or within the follow-up period specified by the protocol, or prescribed in clinical practice, from overdose (whether accidental or intentional), from abuse and from withdrawal.

Adverse events may also occur in screened subjects during any pre-allocation baseline period as a result of a protocol-specified intervention, including washout or discontinuation of usual therapy, diet, placebo treatment or a procedure.

All adverse events will be recorded from the time the consent form is signed through 30 days following cessation of treatment and at each examination on the Adverse Event case report forms/worksheets. The reporting timeframe for adverse events meeting any serious criteria is described in section 6.2.3.1.

Adverse events will not be collected for subjects during the pre-screening period (for determination of archival tissue status) as long as that subject has not undergone any protocol-specified procedure or intervention. If the subject requires a blood draw, fresh tumor biopsy etc., the subject is first required to provide consent to the main study and AEs will be captured according to guidelines for standard AE reporting.

6.2.1 Definition of an Overdose for This Protocol and Reporting of Overdose to the Investigator and to Merck

For purposes of this trial, an overdose will be defined as any dose exceeding the prescribed dose for pembrolizumab by 20% over the prescribed dose. No specific information is available on the treatment of overdose of pembrolizumab. In the event of overdose, pembrolizumab should be discontinued and the subject should be observed closely for signs of toxicity. Appropriate supportive treatment should be provided if clinically indicated.

If an adverse event(s) is associated with (“results from”) the overdose of the investigational product, the adverse event(s) is reported as a serious adverse event, even if no other seriousness criteria are met.

If a dose of the investigational product meeting the protocol definition of overdose is taken without any associated clinical symptoms or abnormal laboratory results, the overdose is reported as a non-serious Event of Clinical Interest (ECI), using the terminology “accidental or intentional overdose without adverse effect.”

All reports of overdose with and without an adverse event must be reported within 24 hours to the Investigator and within 2 working days hours to Merck Global Safety. (Attn: Worldwide Product Safety; [contact])

6.2.2 Reporting of Pregnancy and Lactation to the Investigator and to Merck

Although pregnancy and lactation are not considered adverse events, it is the responsibility of investigators or their designees to report any pregnancy or lactation in a subject (spontaneously reported to them), including the pregnancy of a male subject's female partner that occurs during the trial or within 120 days of completing the trial completing the trial, or 30 days following

cessation of treatment if the subject initiates new anticancer therapy, whichever is earlier. All subjects and female partners of male subjects who become pregnant must be followed to the completion/termination of the pregnancy. Pregnancy outcomes of spontaneous abortion, missed abortion, benign hydatidiform mole, blighted ovum, fetal death, intrauterine death, miscarriage and stillbirth must be reported as serious events (Important Medical Events). If the pregnancy continues to term, the outcome (health of infant) must also be reported.

Such events must be reported within 24 hours to the Investigator and within 2 working days to Merck Global Safety. (Attn: Worldwide Product Safety; [contact])

6.2.3 Immediate Reporting of Adverse Events to the Investigator and to Merck

6.2.3.1 Serious Adverse Events

A serious adverse event is any adverse event occurring at any dose or during any use of the investigational product that:

- Results in death;
- Is life threatening;
- Results in persistent or significant disability/incapacity;
- Results in or prolongs an existing inpatient hospitalization;
- Is a congenital anomaly/birth defect;
- Is a new cancer (that is not a condition of the study);
- Is associated with an overdose;
- Is another important medical event

Progression of the cancer under study is not considered an adverse event unless it results in hospitalization or death.

Any serious adverse event, or follow up to a serious adverse event, including death due to any cause other than progression of the cancer under study that occurs to any subject from the time the consent is signed through 90 days following cessation of treatment, or the initiation of new anti-cancer therapy, whichever is earlier, whether or not related to the investigational product, must be reported within 24 hours to the Investigator and within 2 working days to Merck Global Safety.

Non-serious Events of Clinical Interest will be forwarded to Merck Global Safety and will be handled in the same manner as SAEs.

Additionally, any serious adverse event, considered by an investigator who is a qualified physician to be related to the investigational product that is brought to the attention of the investigator at any time outside of the time period specified in the previous paragraph also must be reported immediately to the Investigator and to Merck.

SAE reports and any other relevant safety information are to be forwarded to the Merck Global Safety [contact]

All subjects with serious adverse events must be followed up for outcome.

6.2.3.2 Events of Clinical Interest

Selected non-serious and serious adverse events are also known as Events of Clinical Interest (ECI) and must be recorded as such on the Adverse Event case report forms/worksheets and reported within 24 hours to the Investigator and within 2 working days to Merck Global Safety. (Attn: Worldwide Product Safety; [contact])

Events of clinical interest for this trial include:

1. an overdose of the investigational product, as defined in Section 6.2.1 - Definition of an Overdose for This Protocol and Reporting of Overdose to the Investigator, that is not associated with clinical symptoms or abnormal laboratory results.
2. an elevated AST or ALT lab value that is greater than or equal to 3X the upper limit of normal and an elevated total bilirubin lab value that is greater than or equal to 2X the upper limit of normal and, at the same time, an alkaline phosphatase lab value that is less than 2X the upper limit of normal, as determined by way of protocol-specified laboratory testing or unscheduled laboratory testing.*

*Note: These criteria are based upon available regulatory guidance documents. The purpose of the criteria is to specify a threshold of abnormal hepatic tests that may require an additional evaluation for an underlying etiology. The trial site guidance for assessment and follow up of these criteria can be found in the Investigator Trial File Binder (or equivalent).

1. Additional adverse events:

A separate guidance document has been provided entitled “Event of Clinical Interest Guidance Document” (previously entitled, “Event of Clinical Interest and Immune-Related Adverse Event Guidance Document”).

ECIs (both non-serious and serious adverse events) identified in this guidance document from the date of first dose through 90 days following cessation of treatment, or 30 days after the initiation of a new anticancer therapy, whichever is earlier, need to be reported within 24 hours to the Investigator and within 2 working days to Merck Global Safety. (Attn: Worldwide Product Safety; [contact]), regardless of attribution to study treatment, consistent with standard SAE reporting guidelines.

Subjects should be assessed for possible ECIs prior to each dose. Lab results should be evaluated and subjects should be asked for signs and symptoms suggestive of an immune-related event. Subjects who develop an ECI thought to be immune-related should have additional testing to rule out other etiologic causes. If lab results or symptoms indicate a possible immune-related ECI, then additional testing should be performed to rule out other etiologic causes. If no other cause is found, then it is assumed to be immune-related.

